#### 7.4 Recruitment

In order to robustly assess the diagnostic accuracy of the tests 1250 patients are required. Recruitment is estimated to be 1 patient per site per month.

#### 8. INFORMED CONSENT

The consultation and recruitment of patients lacking capacity is regulated by different legal jurisdictions across the sites of this study. Practice will adhere to local regulations as outlined below.

Doc No: TM09-LB01 Protocol Version 8.0 Final\_27.05.2021 Page 19 of

It is the responsibility of the Principal Investigator (PI) (or designee) to ensure that informed consent is obtained for each participant. Consent may be obtained by: the PI; an appropriately trained Research Nurse; or medically trained investigator. The PI (or designee) taking informed consent must be suitably qualified and experienced and have been delegated this duty by the Principal Investigator on the delegation log.

A Covering Statement, Patient Information Sheet and Consent/ Declaration Form approved by the Research Ethics Committee (REC) will be provided to study sites. Wherever possible, consent will be taken directly from the patient or from the child's Parent/ Legal Representative.

However, the incapacitated nature of patients in intensive care units will usually preclude obtaining prospective informed consent from participants.

For patients who lack capacity to give informed consent due to, for example, the effects of sedation, infection, delirium and mechanical ventilation; consent or personal / nominated consultee opinion will be obtained as outlined below and in line with the legal requirements for patients without capacity in England and Wales (Mental Capacity Act 2005), and in Northern Ireland (Mental Capacity Act 2016).

At all sites, a deferred consent process will be applied. Samples will be taken as outlined in section 9 of this protocol and will be held at site for up to 7 days pending consent being obtained for inclusion in the study. Once approached for consent, patients or their Parent/ Legal Representative or their Personal/ Nominated Consultee will be allowed up to 2 days to decide whether or not to take part in the study. No samples will be transferred to the Belfast laboratory for testing, or stored at site beyond 7 days, without consent having first been obtained.

## 8.1 Parent/ Legal Representative (Paediatric) – England, Wales and Northern Ireland

The researcher will seek consent from the Parent or Legal Representative of the child. This should normally take place during a face-to-face meeting. An authorised staff member/researcher will describe the trial to the Parent/ Legal Representative, and provide them with a Covering Statement, Information Sheet and Consent Form for the Parent/ Legal Representative (England, Wales and Northern Ireland).

After the researcher has checked that the information sheet is understood, the researcher will invite the Parent/ Legal Representative to sign the consent form and will then countersign it. The original signed form should be provided to the Parent/ Legal Representative. A copy of the form should be placed in the patient's medical notes and a copy filed in the Investigator Site File (ISF).

If the Parent/ Legal Representative is not available at site, the researcher may contact them by telephone and seek verbal agreement. This verbal agreement will be recorded in the Telephone Agreement Form. The Telephone Agreement Form will be signed by a second member of staff who has witnessed the telephone consent. This witness may be a member of the site study team or site medical staff. The original signed form should be provided to the Parent/ Legal Representative. A copy of the Telephone Agreement Form should be placed in the patient's medical notes and a copy filed in the ISF.

If possible, this Telephone Agreement can be followed up by written consent and the original signed consent form provided to the Parent/ Legal Representative. A copy of the form should be placed in the patient's medical notes and a copy filed in the Investigator Site File (ISF).

Doc No: TM09-LB01 Protocol Version 8.0 Final\_27.05.2021 Page 20 of

## 8.2 Personal Consultee (Adults) - England, Wales and Northern Ireland

The researcher will seek advice from a Personal Consultee (who may be a relative, partner or friend of the participant). This should normally take place during a face-to-face meeting. An authorised staff member/researcher will describe the trial to the individual, and provide them with a Covering Statement, Information Sheet and Declaration Form for Personal Consultee (England, Wales and Northern Ireland). The researcher will seek their views about whether the patient should take part in the study. They will be asked about their opinion of the wishes and feelings of the patient if they had capacity.

After the researcher has checked that the information sheet is understood, the researcher will invite the Personal Consultee to sign the declaration form and will then countersign it. The original signed form should be provided to the Personal Consultee. A copy of the form should be placed in the patient's medical notes and a copy filed in the Investigator Site File (ISF).

If the Personal Consultee is not available at site, the researcher may contact the Personal Consultee by telephone and seek verbal agreement. This verbal agreement will be recorded in the Telephone Agreement Form. The Telephone Agreement Form will be signed by a second member of staff who has witnessed the telephone consent. This witness may be a member of the site study team or site medical staff. The original signed form should be provided to the Personal Consultee. A copy of the Telephone Agreement Form should be placed in the patient's medical notes and a copy filed in the ISF.

If possible, this Telephone Agreement can be followed up by written consent and the original signed declaration form should be provided to the Personal Consultee. A copy of the form should be placed in the patient's medical notes and a copy filed in the Investigator Site File (ISF).

## 8.3 Nominated Consultee (Adults) - Approval by a Registered Medical Practitioner (RMP) - England, Wales and Northern Ireland

In the event that there is no Personal Consultee for sites in England, Wales and Northern Ireland, authorisation to recruit the patient will be sought from a RMP (a doctor unrelated to the study conduct). The RMP will be informed about the trial by a member of the research team and given a copy of the Registered Medical Practitioner Form (England, Wales and Northern Ireland) and a copy of the Information Sheet. If the RMP decides that the patient is suitable for entry into the study they will be asked to complete the relevant authorisation form. The original signed form should be provided to the RMP. A copy of the authorisation form should be placed in the patient's medical notes and a copy filed in the ISF. In the event that a Personal Consultee is identified after the RMP has provided their opinion, the above process for Personal Consultee will be followed and all forms will be filed as instructed above.

In the event that a patient dies subsequent to clinical samples being obtained but prior to consent having been obtained, authorisation to recruit the patient may be sought from a RMP. The RMP will be informed about the trial by a member of the research team and given a copy of the Registered Medical Practitioner Form (England, Wales and Northern Ireland) and a copy of the Information Sheet. If the RMP decides that the patient is suitable for entry into the study they will be asked to complete the relevant authorisation form. The original signed form should be provided to the RMP. A copy of the authorisation form should be placed in the patient's medical notes and a copy filed in the ISF.

#### 8.4 Patient Consent to Continue (Adults) - England, Wales and Northern Ireland

Site research staff as delegated by the PI will assess whether the patient has regained capacity to give informed consent. Patients may be approached to obtain permission to continue in the study either whilst still in ICU or within 96hrs after their discharge from ICU. In

Doc No: TM09-LB01 Protocol Version 8.0 Final\_27.05.2021 Page 21 of

the event that the patient does not regain capacity, or staff have been unable to obtain consent to continue, the opinion provided by the Personal/Nominated Consultee will continue.

The consent to continue process will include providing the Covering Statement, Patient Information Sheet and Consent Form and allowing sufficient time for the patient to understand the material and ask questions. If the patient agrees to continue in the study they will be asked to sign the Consent Form which will then be counter signed by a member of the research team. The original signed form should be provided to the patient. A copy of the Consent Form should be placed in the patient's medical notes and a copy filed in the ISF.

If the participant declines on-going participation in the study this will be noted in the CRF and no further follow-up will take place. Blood samples and data collected up until that point will be pseudonymised before returning to Queen's University Belfast and the co-ordinating centre respectively.

#### 8.5 Withdrawal of Consent

Participants, their Parent/ Legal Representative, Personal/ Nominated Consultee or Registered Medical Practitioner may withdraw the patient from the study at any time without prejudice. In the event of a request to withdraw, participants will be given the option to withdraw consent from part or all of the study, including long term storage of blood samples. In the event of a request to withdraw from the study anonymised data recorded up to the point of withdrawal will be included in the study analysis unless requested otherwise. We will seek permission to continue to collect patient data during the patient's hospital admission and to follow up to ascertain their long term health status using NHS/HSC hospital information systems, NHS Digital or via their GP (if they have been discharged).

Doc No: TM09-LB01 Protocol Version 8.0 Final\_27.05.2021 Page 22 of

## 9. SCHEDULE OF ASSESSMENTS AND STUDY PROCEDURES

#### 9.1 Schedule of Assessments

All patients will be evaluated during the study and data collected at each of the following timepoints. For routinely collected clinical data the NHS record will be the source document and for study specific clinical measurements the CRF will be the source document, with the exception of the EQ-5D-5L which may be originally completed on a paper worksheet.

#### **Baseline**

- · Age and gender
- Inclusion and exclusion criteria.
- Hospital admission date and location of patient prior to admission
- ICU admission date and main diagnosis
- Date research blood sample obtained for index tests and reference standard test
- Candida colonisation status at non-sterile anatomic sites, as determined by local laboratory testing in the course of normal clinical care
- Drug, dose and start date of systemic antifungal therapy
- Indication for starting antifungal therapy (e.g. for suspected or proven Candida infection)
- Patient characteristics triggering suspicion of Candida infection (e.g. fever, leucocytosis, increasing inotrope requirement, new or worsening organ failure, signs of intra-abdominal sepsis, failure to demonstrate improvement with broad-spectrum antibacterial treatment)
- Severity of illness indicators: APACHE II on admission to ICU (ICNARC case mix programme number) and SOFA score (adults) & PELOD-2 score (children- when available) on the day of recruitment.

#### Index and Reference Test Data

#### Assessed by central laboratory research staff (blinded to reference test results):

- Outcome of each index test in all participants sampled. Because the classification of index test results requires no subjective assessment, staff completing a given index test will not be blinded to the results of other index tests. However, staff completing index tests will be blinded to the results of reference tests.
- Laboratory tests to support classification of participants using a constructed reference standard for probable Candida infection.
  - o Mannan antigen
  - o Anti-mannan antibody

#### Assessed by site staff:

- Outcome of reference standard for proven fungal disease, as applied to Candida infection (based on data collected/laboratory results from day of enrolment). This will comprise:
  - Blood culture, yielding Candida species, drawn within 24 hours of starting antifungal treatment; AND/OR
  - Culture showing Candida species in specimen obtained by a sterile procedure from a normally sterile site (excluding urine). This includes a drain placed within 24 hours before sampling.

A blood culture will be drawn from each participant within 24 hours of starting antifungal treatment, usually in the course of standard clinical care, in accordance with usual practice for patients started on antifungal treatment. Specimens from

Doc No: TM09-LB01 Protocol Version 8.0 Final\_27.05.2021 Page 23 of

other normally sterile sites will be obtained as considered appropriate by the attending physician in the course of normal clinical care.

- Outcome of any blood cultures yielding Candida species taken +/-7 days from obtaining the research blood sample.
- Host factors and clinical findings pertinent to classification using a recently constructed consensus definition for probable Candida infection. Data collection for this classification will comprise:

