## 3.2.2 New rapid tests offer an opportunity for timely treatment decisions to avoid unnecessary treatment

Tests recently introduced to market, such as the new PCR-based tests, as well as BDG tests, can be completed within one working day and offer the opportunity to influence prescribing decisions at an early time-point. Prior to commercialisation of these Candida PCR tests, the performance of a variety of in-house assays has been described in small series. Collectively,

Doc No: TM09-LB01 Protocol Version 8.0 Final\_27.05.2021 Page 13 of

in meta-analyses, these have shown promising accuracy and it is assumed that commercial tests of a similar nature will perform similarly [9]. BDG is a biomarker that has demonstrable potential for improving the diagnosis of a number of fungal infections, in various populations. including candidaemia and deep-seated candidiasis [10-13].

The most obvious advantage these new tests bring over current culture-based techniques is their speed. Although blood cultures tend to become positive after 2-3 days at least 5-days must lapse before they can be declared negative. After 5-days of presumptive antifungal treatment, even though the patient may have improved for a variety of reasons, doctors are usually unwilling to stop treatment since it is uncertain whether the patient's response is due to antifungal treatment or other factors. By comparison, a negative result obtained within 24hrs of starting presumptive treatment is much more likely to guide antifungal treatment, before the patient is seen to have improved. Hence tests that bring timely results are better able to influence decision-making and redirect conventional practices. The new tests may also bring improved sensitivity, hence higher negative predictive values, than conventional culture methods.

Diagnostic accuracy data currently available for these tests consists of small studies in heterogeneous patient groups. While their performance has been assessed in meta-analyses, it is impossible to be certain that the findings from assimilating low-to-moderate quality data in this way are correct. The diagnostic test accuracy study we propose here will meet this need and offer a pathway to practice change and better targeted antifungal prescribing.

Doc No: TM09-LB01 Protocol Version 8.0 Final\_27.05.2021 Page 14 of

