#### 7.1.1 Inclusion criteria:

- 1. Adults and children >4 weeks old.
- 2. Admitted to a UK ICU (level 2 or 3).
- 3. Prescribed systemic antifungal therapy, for suspected or confirmed Candida infection, during the preceding 24 hours.

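### A positive blood culture that prompted treatment usually falls outside the 24-hour limb of the proven reference standard, so a patient with documented candidaemia can be analysed as uninfected in the primary NPV analysis

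*Protocol*

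**What the plan says.** Section 5.1 makes NPV the primary outcome, judged against the consensus standard for proven disease. Section 9.1 (Assessed by site staff) defines that standard by two limbs joined by AND/OR:

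- **Blood-culture limb:** "Blood culture, yielding Candida species, drawn within 24 hours of starting antifungal treatment".
- **Sterile-site limb:** a positive Candida culture from a normally sterile site, with no 24-hour condition of its own.

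A clause over both limbs says that the standard is "based on data collected/laboratory results from day of enrolment".

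A separate item after the definition collects "Outcome of any blood cultures yielding Candida species taken +/-7 days from obtaining the research blood sample". No section says how this item enters the proven classification.

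The third inclusion criterion (7.1.1) reads "Prescribed systemic antifungal therapy, for suspected or confirmed Candida infection, during the preceding 24 hours", and the baseline data include whether the indication was suspected or proven infection. Section 3.2.2 says that "blood cultures tend to become positive after 2-3 days".

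**The concern.** A patient treated because a blood culture grew Candida is the clearest case of infection that the study will enrol. Yet the culture that established the diagnosis is the one that the definition tends to leave out. The patient then counts as proven only through a repeat blood culture near the start of treatment, possibly taken after the first doses, or through a sterile-site specimen.

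The error works in two directions. An index-positive patient of this kind becomes an apparent false positive and lowers specificity and PPV. An index-negative one becomes an apparent true negative and raises NPV, which favours the test on the primary outcome. The same patient would also be counted as treated unnecessarily under secondary outcome (iii), which is derived from the reference standards.

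**Working it through.** **1. Timing.** A typical time to positivity of 2-3 days is 48-72 hours. If treatment waited for that result, the culture was drawn 48-72 hours before treatment. That exceeds 24 hours whether the window is read as before, after or either side of treatment start, a direction the protocol does not state. It also normally precedes the day of enrolment.

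Would the data already collected include it? The paired culture is within 24 hours of treatment start, and the research sample is within 24 hours of the paired culture (section 9.2.1). The prompting culture is therefore at most about 3 + 1 + 1 = 5 days before the research sample, which is inside the 7 days.

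**2. The plan's own figures (section 11.1).**
- 1250 × 0.95 = 1187.5, so 1188 evaluable; 1188 × 0.04 = 47.5, so 48 infected and 1140 uninfected.
- 44/48 = 91.7%, exact 95% CI 80.0% to 97.7%, as stated.
- Expected index-negatives: 1188 × (0.96 × 0.92 + 0.04 × 0.05) = 1051.6. An exact two-sided 5% test of NPV against 99% with 1052 negatives allows at most 4 false negatives and has power 90.7%, consistent with the stated 90%.

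**3. Effect of misclassification.** Let m infected patients be classed as uninfected, with index sensitivity s among them. Other inputs are from section 11.1: specificity 92%, and sensitivity 95% in the remaining infected. The values m = 5 and 12 (about 10% and 25% of 48) and s = 80% are assumptions.

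- Counted infected = 48 − m
- Apparent specificity = (1140 × 0.92 + m(1 − s)) / (1140 + m)
- Hidden misses = m(1 − s)
- Counted misses = (48 − m) × 0.05
- Index-negatives = 1048.8 + counted misses + hidden misses
- Apparent NPV = (1048.8 + hidden misses) / index-negatives
- NPV against true infection = 1048.8 / index-negatives

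| m | s | Counted infected | Apparent specificity | Hidden misses | Counted misses | Apparent NPV | True NPV |
|---|---|---|---|---|---|---|---|
| 0 | 95% | 48 | 92.0% | 0 | 2.4 | 99.77% | 99.77% |
| 5 | 95% | 43 | 1049.05/1145 = 91.6% | 0.25 | 2.15 | 99.80% | 99.77% |
| 12 | 95% | 36 | 1049.4/1152 = 91.1% | 0.6 | 1.8 | 99.83% | 99.77% |
| 5 | 80% | 43 | 1049.8/1145 = 91.7% | 1.0 | 2.15 | 99.80% | 99.70% |
| 12 | 80% | 36 | 1051.2/1152 = 91.3% | 2.4 | 1.8 | 99.83% | 99.60% |

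In the last row the expected misses are 1.8 + 2.4 = 4.2, of which 1.8 are counted, against a limit of 4.

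**4. Secondary outcome (iii).** The apparent share without proven infection rises from 1140/1188 = 96.0% to 1145/1188 = 96.4% (m = 5) or 1152/1188 = 97.0% (m = 12).

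**The case against.** The affected group may be small. Section 7.3 describes patients started presumptively, and the rationale is about presumptive treatment. A presumptively treated patient whose culture from around treatment start later grows Candida is counted. To be misclassified, a patient must have had treatment wait for a result, then a negative repeat blood culture in the window and no positive sterile-site culture. The 2-3 days is a tendency, so a fast-growing culture could fall within 24 hours. A narrow window also ties the reference to the moment of the index sample, which is a defensible aim. Section 11.2 admits that the standard has imperfect sensitivity, and the proven + probable analysis and the latent class models may recover some of these patients. All of this stands, and it limits the size.

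It does not remove the point. Section 11.2 speaks of a standard that fails to detect disease and foresees underestimated specificity. Here a positive result exists and the definition sets it aside, and the effect on NPV is not mentioned. The other analyses are secondary or exploratory.

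A reader might infer several stronger points that the protocol does not support:

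- **That only blood cultures from the 24-hour window count.** The sterile-site limb is an alternative route to proven.
- **That the sterile-site limb has no time limit.** The enrolment-day clause covers both limbs. Its meaning is unclear, which is a different fault.
- **That sensitivity would drop to 32/36 = 88.9%, below the 90% cut-off.** This keeps all 4 false negatives after removing 12 infected patients. At 95% sensitivity, 36 infected give about 1.8.
- **That recording "Drug, dose and start date of systemic antifungal therapy" means clock times are not captured.** The protocol lists data items; field formats belong to the CRF, which is not shown.

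**Conclusion.** The concern holds for the blood-culture limb. Followed as written, section 9.1 can class a patient with documented candidaemia as uninfected for the primary outcome, although sections 7.1.1 and 3.2.2 imply that such patients will be enrolled and that their diagnostic culture usually predates the window.

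The number affected cannot be obtained from the protocol. Assuming 5-12 of 48, apparent specificity drops by about 0.4 to 0.9 percentage points at 95% sensitivity. Hidden misses are 0.25-0.6 at the protocol's own sensitivity, and 1.0-2.4 if the index tests detect only 80% of these patients.

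The bias in NPV is small in absolute terms. It would be wrong to infer that the 99% criterion is shown to fail. In an extreme case, with 40% of the infected affected and 50% of those detected, NPV against true infection would be 1048.8/(1048.8 + 1.44 + 9.6) = 98.96%, and nothing in the protocol points to values that extreme. The point matters because the error favours the test on a primary outcome that tolerates only about 4 misses, and because it costs some of the few infected cases.

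**What to change.** In section 9.1, state that a Candida-positive blood culture drawn before treatment and within the 7 days before the research sample counts as proven, expressly including the culture that prompted treatment.

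Reconcile this with the enrolment-day clause, and say what that clause means as the start and end of the window for each limb. Read strictly, it could exclude even a culture inside the 24 hours if that was drawn the day before enrolment.

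Report two sensitivity analyses: the current 24-hour definition, and one that counts any positive blood culture within 7 days either side of the research sample. The full symmetric window is better kept out of the primary definition, because its later half admits new infections.

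The cost is mainly wording, since these blood-culture results are already a collected item. The 7-day item covers blood cultures only, so a window for the sterile-site limb has to be set separately. Because this changes the primary reference standard during the study, it should be settled before the index results are compared with it. The small downside is that a few earlier candidaemias that had cleared by the research sample may count as infected; the 24-hour sensitivity analysis shows how much that matters.

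### The proven reference standard gives positive blood cultures drawn outside 24 h of treatment start no role, so a participant with culture-documented candidaemia can be scored uninfected in the primary analysis

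*Protocol*

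**What the plan says.** Protocol Section 5.1 bases the primary outcome, NPV of each index test, on the proven standard alone. Section 9.1, under the items assessed by site staff, lists what that standard comprises:

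- **Blood limb:** "Blood culture, yielding Candida species, drawn within 24 hours of starting antifungal treatment".
- **Sterile-site limb, joined by and/or:** "Culture showing Candida species in specimen obtained by a sterile procedure from a normally sterile site (excluding urine"). It has no time window. The specimen paragraph that follows speaks of other sterile sites, so blood belongs to the first limb; otherwise the first limb would be redundant.
- **Time anchor on the whole item:** "based on data collected/laboratory results from day of enrolment".
- **In-window culture for all:** "A blood culture will be drawn from each participant within 24 hours of starting antifungal treatment".

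A separate bullet, outside that definition, collects "Outcome of any blood cultures yielding Candida species taken +/-7 days from obtaining the research blood sample". Nothing in the protocol says how a positive result there is classified.

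Three other places bear on the point. Section 7.1.1 admits patients who meet "Prescribed systemic antifungal therapy, for suspected or confirmed Candida infection, during the preceding 24 hours". The baseline list in Section 9.1 records "Indication for starting antifungal therapy (e.g. for suspected or proven Candida infection"). Section 3.2.2 states "Although blood cultures tend to become positive after 2-3 days".

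**The concern.** Taken together, these statements leave a gap. If a blood culture takes 2-3 days to turn positive, one whose result led to treatment will usually have been drawn more than 24 h before the first dose. It is then outside the window even if the window runs in both directions. The same holds for a culture drawn two days before an empirical start that turns positive afterwards. The first kind of patient may carry a baseline indication of proven infection and still be reference-negative.

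Once scored uninfected, such a patient distorts the results in one of two ways:

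- **Index-negative:** counted as a true negative, so NPV is too high.
- **Index-positive:** counted as a false positive, so specificity and PPV are too low.

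Either way, under the proven standard the patient's treatment counts as unnecessary. That proportion is derived from the reference standards (Sections 5.2(iii) and 11.4.1). The study is meant to support stopping antifungals, so an NPV error in the favourable direction is the one to guard against.

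**Working it through.** **Inputs (Section 11.1).** 1188 evaluable participants, prevalence 4%, sensitivity 95%, specificity 92%.

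**Step 1: reproduce the plan.**
- Infected: 1188 × 0.04 = 47.52. Uninfected: 1140.48.
- Expected false negatives: 47.52 × 0.05 = 2.376. True negatives: 1140.48 × 0.92 = 1049.24. Index-negatives: 1051.6.
- NPV: 1049.24 / 1051.6 = 99.77%.
- Exact test of NPV above 99% on 1052 negatives. The alpha is not stated; one-sided 2.5% is assumed. P(4 or fewer false negatives at a 1% rate) = 0.020 and P(5 or fewer) = 0.049, so the test passes with at most 4. Power = 90.7%, matching the stated 90%.
- Exact 95% CI for 44/48: 80.0% to 97.7%, as stated.

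The sample-size figures are sound and are not in question.

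**Step 2: move k infected participants to the uninfected group.** Let q be the share of them that is index-negative. Neither k nor q is in the documents; both are assumed.
- False negatives as scored: (47.52 − k) × 0.05. Hidden false negatives: k × q.
- Index-negatives: 1049.24 + scored + hidden.
- NPV as scored = 1 − scored / index-negatives. NPV with all counted = 1 − (scored + hidden) / index-negatives.
- Chance of passing: Poisson P(4 or fewer), with mean equal to the scored or to the total false negatives.

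| k | q | False negatives scored / all | NPV scored / all | Pass scored / all |
|---|---|---|---|---|
| 2 | 5% | 2.28 / 2.38 | 99.78% / 99.77% | 91.9% / 90.7% |
| 5 | 5% | 2.13 / 2.38 | 99.80% / 99.77% | 93.5% / 90.7% |
| 10 | 5% | 1.88 / 2.38 | 99.82% / 99.77% | 95.8% / 90.7% |
| 5 | 25% | 2.13 / 3.38 | 99.80% / 99.68% | 93.5% / 75% |
| 5 | 50% | 2.13 / 4.63 | 99.80% / 99.56% | 93.5% / 51% |
| 10 | 25% | 1.88 / 4.38 | 99.82% / 99.58% | 95.8% / 56% |
| 10 | 50% | 1.88 / 6.88 | 99.82% / 99.35% | 95.8% / 18% |

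The q = 5% rows use the plan's own sensitivity.

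**Step 3: the other measures at q = 5%.**
- Observed prevalence, (47.52 − k) / 1188: 4.0% falls to 3.6% (k = 5) or 3.2% (k = 10).
- Specificity, (1049.24 + 0.05k) / (1140.48 + k): 92.0% falls to 91.6% or 91.2%.
- PPV, with true positives (47.52 − k) × 0.95 and false positives 91.24 + 0.95k: 33.1% falls to 29.6% or 26.1%.
- Share without proven infection, hence counted as treated unnecessarily: 96.0% rises to 96.4% or 96.8%.

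**Step 4: NPV at a fixed prevalence.** Section 11.2 refers to predictive values at a specified prevalence. If NPV is built from sensitivity and specificity at 4%, then k = 10 and q = 5% gives 0.9124 × 0.96 / (0.9124 × 0.96 + 0.05 × 0.04) = 99.77%, unchanged. On that reading, bias in NPV again needs lower index sensitivity in these patients.

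**The case against.** **Misclassification is conditional.** Every participant has a culture in the window, and the sterile-site limb has no time limit. An error needs the first to be negative and the second to give no positive. Since the window has no stated direction, a culture drawn up to 24 h before the first dose can be read as counting. All of this stands. A reader might infer that any candidaemia shown by an earlier culture is scored as no infection; the text does not support that.

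**Frequency is unknown.** A reader might also infer that the excluded culture is often the one that prompted treatment. No figure supports this. Section 7.3 describes presumptive starts, and Section 3.2.1 says treatment commonly begins on little or no evidence. This limits the likely number but does not remove the mechanism, because confirmed cases are eligible.

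**The large effects come from q.** Index-negative shares of 25-50% are 5 to 10 times the plan's 5%, and nothing in the documents supports them. These patients are selected for a negative in-window culture, and the research sample is paired with a standard-care culture (Section 9.2.1), so lower index sensitivity is plausible, but it is not shown. Even at k = 10 and q = 50%, NPV with all false negatives counted is 99.35%, above both the 99% criterion and the surveyed 98%.

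**Imperfect sensitivity is acknowledged.** Section 11.2 says so, adds a proven-plus-probable analysis and presents a range. That may recover some cases. It is secondary, however, and the data listed for the probable category do not include out-of-window blood cultures, so recovery is not assured.

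**The window keeps index and reference samples close in time.** That is a legitimate design reason and argues for keeping the 24 h definition in the report.

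**The SAP may settle it.** An unseen SAP could give the ±7-day cultures a role. The protocol nonetheless fixes the definition for the primary outcome, and as fixed it omits them.

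**Conclusion.** The concern holds in conditional form. As written, a participant whose only positive blood culture was drawn more than 24 h before the first dose, with a negative in-window culture and no other positive sterile site, can be scored uninfected in the primary analysis.

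At the plan's 95% sensitivity, and for an assumed 5-10 such patients, NPV is overstated by 0.02-0.05 percentage points and the chance of passing by 3-5 points. PPV and the case count move more. A serious effect on the NPV conclusion requires index sensitivity far below the plan's value in these patients, which is an assumption. All pass probabilities rest on a one-sided 2.5% exact test, which reproduces the stated power but is not itself stated.

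The definition should be settled before analysis, because it governs the primary outcome and the data to resolve it are already collected. The documents do not show that the primary result is invalid.

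**What to change.** 1. State whether the 24 h window runs before the first dose, after it, or both.
2. Count as proven a Candida-positive blood culture drawn before treatment start and within the 7 days before the research sample, for the episode being treated. The episode must be specified: exclusion criterion 1 (Section 7.1.2) does not rule out an earlier course of up to 24 h, or one that ended more than 7 days before.
3. Report the accuracy measures under this definition and under the current 24 h one, with the number of participants reclassified and their index results. That replaces the assumed k and q with observed values.

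**Cost.** A short amendment to the definition, repeated in the SAP, and re-derivation of one variable from data already collected. There is a small downside: a candidaemia that cleared before the research sample would count as a false negative, and index and reference samples would be less contemporaneous. That is why both definitions should be reported.
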